Effect of genotype on Resting State Connectivity during Methamphetamine Administration

[figure not shown]
PI: [name], MD

NCT 03973489

Protocol Version: 11-29-2021

Relevance to Veterans and the VA Mission: Methamphetamine is one of the most common addictive disorders among veterans today. Research seeking to understand the causes and maintenance of addiction are highly relevant to the VA's mission of serving the healthcare needs of the Veteran.

Specific Aims and Rationale: This proposal will determine the effect of a common variant (CV) synonymous

single nucleotide polymorphism (SNP) of the gene for the human trace amine associated receptor 1(TAAR1) on the neural and behavioral response of subjects with methamphetamine (MA) use disorder (MUD) to acute MA administration. The SNP (rs8192620 on human [GRCh38.p7] chromosome 6 at 132,645,140 bp in htaar1, allelic frequency 22%) results from a change of adenine to guanine in a valine codon at amino acid 288 (v288v). MA is a potent agonist at the TAAR1 receptor (Reese et al., 2007), in addition to its actions at the dopamine transporter (Elliott and Beveridge, 2005) and the vesicular monoamine transporter (Fleckenstein et al., 2009). In rodents, a decrease in TAAR1 expression or nonfunctional TAAR1 receptor is associated with an increase in striatal dopamine (DA) signaling (Espinoza et al., 2015).

The scientific premise of this project is based on 1) our preliminary findings that support a model that the CV alters RSFC of the striatum, a dopaminergic terminal region, and associated behavior in chronic MUD, 2) published reports that delineate the effect of TAAR1 on DA signaling and 3) preclinical evidence that TAAR1 influences sensitivity to rewarding and aversive effects of MA.

Furthermore, this proposal will address guestions that have important implications for understanding and treating patients with MUD, as the TAAR1 receptor is implicated in MA self-administration. As an allele of the murine TAAR1 gene associated with an inactive receptor leads to increased MA intake in homozygotes (Harkness et al., 2015; Phillips and Shabani, 2015), it is critically important to study the feasibility of exploiting human variant htaar1.

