We propose a model (Figure 1) based on this premise that makes testable predictions about the interaction of the CV with chronic and acute MA administration in MUD. Our preliminary data show that the CV causes overexpression of TAAR1 in cell culture. Stimulation of the TAAR1 receptor decreases dopaminergic signaling in mesocorticolimbic and corticostriatal networks (Pei et al., 2016;Berry et al., 2017). We propose that this effect in conjunction with chronic MA use causes neuroadaptations that result in the increased striato- and corticolimbic RSFC as well as increased drug craving observed in MUD subjects with the CV. We can indirectly test the hypothesis of decreased DA release due to ever-expression via MA administration. The effect of acute MA administration on RSFC in humans is not known but acute administration of S-amphetamine

(Schrantee et al., 2016) and methylphenidate (Konova et al., 2013) reduce RSFC in salience attribution and default mode networks presumably via increased DA release. Stimulation of over-expressed TAAR1 should blunt this effect in CV carrying individuals compared to WT. There are no published reports on neural effects of the interaction between either chronic or acute MA administration and *htaar1* genotype in humans, therefore this proposal represents a unique opportunity to determine whether the RSFC response to acute MA administration in humans is mediated by genotype.

In Specific Aim 1 (SA 1), we will confirm and extend our preliminary RSFC findings in *chronic* MUD using seed-based and data-driven precision brain mapping approaches. The latter are made possible by extended (40 minute) acquisition of functional connectivity data. We will investigate genotype and drug x genotype interactions with full connectivity matrices as well as topological RSFC measures including connection density and strength, network segregation, global efficiency, rich club coefficients, and global segregation in MA users at baseline and after MA administration. In SA 2, we will examine how htaar1 genotype modifies the effects of acute MA administration on neural and behavioral measures in MUD. This provides an indirect test of Figure 1A that genotype modifies TAAR1 expression in the ventral tegmental area (VTA) and thus DA release in the striatum.

SA 1. Determine the influence of *htaar1* CV vs. wild type (WT) genotype on RSFC and craving in *chronic* MUD.

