Hypothesis 1: CV vs. WT will exhibit higher cortico-striatal and striato-limbic and intrastriatal RSFC (Figure 1B and C: Base) and report higher craving for MA at baseline.

SA 2: Determine the effect of *acute* oral MA or placebo (PBO) administration on the interaction of *htaar1* CV vs. WT genotype on RSFC, craving, cognitive control, attention and subjective experience in MUD.

Hypothesis 2: Acute MA administration will lower RSFC in both genotypes, with a blunted decrease in the CV group (Figure 1C: MA and PBO).

Hypothesis 3: The CV group will exhibit, compared to WT, blunted effect of MA administration on craving, subjective experience and tests of attention and cognitive control.

Experimental Design:

Recruitment: MUD and control subjects will be recruited by advertisement from VAPORHCS, OHSU, community assistance programs. Advertisements will also be posted online externally utilizing Craigslist, the VAPORHCS web page, the quarterly newsletter (Veteran Connection), the VA Facebook page OHSU's Research Opportunities pages, the OHSU website (MARC page or dedicated lab page), Indeed.com, Ziprecruiter, Google Jobs, Localwise.com, Skoll.org, and community news publications (Street Roots, Portland Mercury, Willamette Weekly and possibly others). Approved flyers will be distributed throughout the community (retail locations, community assistance programs, primary care clinics, emergency departments, dental clinics, community outreach programs). All Craigslist ads, other job boards and social media will have email reply turned off so that potential participants will have to call the study team. Facebook posts will have a link to a PDF of the approved flyer, which will direct any subjects to contact the study team. All content published for both internal and external promotion will utilize the approved flyer or other approved language so that anyone interested in the study will have to call the study team for more information. Newspaper, job board and social media ads will utilize the approved Craigslist ad language unless other language is specifically approved. If potential subjects are referred by their VA providers, the provider will first ask permission from the subject to discuss the research project. If the subject gives permission, the provider will document this either in a CPRS note or encrypted email to the study team. VA providers may also send out our approved flyer with their regular occurring mail outs to their clients.

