RSFC time courses will also be normalized and detrended, and signals correlated with motion, mean white matter, mean ventricle and mean brain, along with their temporal derivatives, will be removed through linear regression. Motion regression will include 6 parameter displacement time courses plus their derivatives and squares; only frames where displacement is below standard cutoffs will be included in the regression. Postregression time courses will be band-pass filtered between 0.009 and 0.08 Hz. Signal from ventricular regions and from white matter will be removed from the data through linear regression estimations. Specific Outcome Measures and Hypotheses: We will use a mixed effects model with one between-subjects variable (genotype) to investigate outcome variables. Precision brain mapping (Gordon et al., 2017) allows these analyses to occur between subjects with excellent power. SA 1 and Hy 1 predicts a significant effect of genotype on baseline intrastriatal connectivity and craving. Subsequent analyses can be conducted in several ways based on these data. We will use both a hypothesis driven seed region approach based on a priori region of interests (ROIs) of the VS, midbrain, dorsolateral prefrontal cortex, and ventromedial prefrontal cortex and a data driven approach based on a fcMRI correlation matrix. Bivariate correlations between the average BOLD signals from these regions will provide connectivity estimates. In addition to our planned seed-based comparisons, we will secondarily investigate whole brain connectivity with pair-wise correlations between each ROI within the several sets of functionally-defined parcellations and subcortical ROIs. forming correlation matrices. We use ROIs from the highly cited and utilized Gordon Parcellation (Schaefer et al., 2017;Gordon et al., 2016), a set of 333 ROIs supplemented by a set of 19 subcortical regions defined by FreeSurfer (Fischl, 2012) during pre-processing. Correlations will be Fisher's Z transformed to correct for non-normality and to allow averaging across groups. Sub-matrices will be derived using InfoMap and sub-graphs identified with known cerebral networks (Fortunato and Hric, 2016;Rosvall and Bergstrom, 2008). Correlation matrices will provide access to specific circuits within individuals and will be utilized to describe and provide specific predefined network strengths and characteristics (e.g. default-mode, fronto-parietal, dorsal attention and salience attribution), as well as topological properties for each individual and genotype group. Statistical analysis for these effects are modeled after Feczko et al. (2017) and Eggebrecht et al. (2017) and are detailed in 4.4 Statistical Design and Power. Such an approach allows us to consider individual differences in the functional neuroanatomy, as well as investigate genotype-MA interactions. Topological measures include: connection density and strength, network segregation, global efficiency, rich club coefficients, and global segregation; "hub" measurements will include hub degree, strength, within module z-score, and participation coefficient. SA 2 and Hy 2 predicts a significant genotype x acute drug administration interaction, specifically that acute MA administration will have a blunted effect in the CV group. For Hy 2 and Hy 3 our primary analytic model

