
will again be a linear mixed effects analysis, with two within-subjects factors (scan day and drug) with either RSFC or behavioral measures included as dependent variables and main effects of genotype and their interaction as primary predictors. Post-hoc analyses will be used as necessary to examine effects for individual outcomes and to estimate allelic frequency associations as well as sex by genotype interactions. **HY 3** would be confirmed by finding a blunted effect of MA administration on reports of euphoria and craving and on effects on attention and cognitive control in the CV group.

Interpretation of Results: Higher RSFC in CV vs. WT would be consistent with our hypothesis that neuroadaptations to *chronic* MA use interact with genotype to differentially alter striatal connectivity. A blunted effect of *acute* MA on RSFC in CV vs. WT groups would be consistent with our hypothesis that the CV, v288v, is associated with increased TAAR1 signaling that diminishes the corticostriatal effects of MA. The lack of group differences would suggest that genotype does not moderate the MA effects and opposing results may indicate compensatory mechanisms in those with the *htaar1* variant.

Risks to Subjects

All study data derived from subject procedures (including tasks, rating scales, screening interview questionnaires and MRI scan) are obtained specifically for research purposes and not for treatment. Urine and blood specimens will be analyzed by the VA lab and destroyed according to protocol. UAs will be obtained and analyzed by the research team or the VA lab and will be destroyed according to protocol. Two cheek swabs will be taken, the first will be analyzed for genotype and then destroyed. The second will be taken during Visit 2 and banked for future research. MRI scans are obtained at the Advanced Imaging Research Center at OHSU and stored on a disk partition specific to this study and only accessible by study staff. The imaging data are downloaded to image analysis workstations located in the [name] Lab at the VA and raw images are archived on a dedicated server at the OHSU Advanced Computing Center (ACC). Coded data may be processed temporarily on additional OHSU servers in the future.

Risks of Questionnaires, Computer Tasks and Cognitive/Neuropsychological Testing: Participants may become upset or frustrated while answering personal questions during the interview or during administration of the neuropsychological tests

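### Four diagnosis-by-genotype cells are enrolled and dosed, but the primary models in the supplied text contain only genotype, so the analysis population is unstated and the chronic-use reading has no diagnosis-by-genotype contrast behind it

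*Combined protocol and SAP*

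**What the plan says.** **Design.** Recruitment and Enrollment set out four groups, MUD and control by WT and CV, each to reach 18 completers. MA Administration and Randomization gives every Part 2 participant active drug on one visit and placebo on the other, with no restriction by diagnosis. MA Metabolites confirms that controls receive study drug.

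**Aims.** These are worded for MUD. Specific Aims and Rationale speaks of the "behavioral response of subjects with methamphetamine (MA) use disorder (MUD) to acute MA administration". The measures listed under Specific Aim 1 end with "global segregation in MA users at baseline and after MA administration". Specific Aim 2 concerns "genotype on RSFC, craving, cognitive control, attention and subjective experience in MUD".

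**Models.** Specific Outcome Measures and Hypotheses states: "We will use a mixed effects model with one between-subjects variable (genotype) to investigate outcome variables". For Hypotheses 2 and 3 it adds scan day and drug as within-subject factors, with "main effects of genotype and their interaction as primary predictors". The only other between-subject term is a post hoc sex-by-genotype interaction. For the network effects, the statistical detail is referred to a section 4.4, which is not in the supplied text.

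**Inference.** The proposed model holds that "this effect in conjunction with chronic MA use causes neuroadaptations that result in the increased striato- and corticolimbic RSFC". Interpretation of Results takes higher resting-state functional connectivity (RSFC) in CV than WT as consistent with the hypothesis that neuroadaptations to chronic use "interact with genotype to differentially alter striatal connectivity".

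**Pilots.** In Specific Aim 1 the sponsor writes "we will confirm and extend our preliminary RSFC findings in" chronic MUD. Preliminary study PS1 fitted a genotype-by-group term and found no association in controls (fold change 0.99, p = 0.94). The genotype result that PS2 reports for RSFC is a group-by-genotype interaction (p < 0.005).

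**The concern.** Two things are left open.

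First, a model with genotype as its one between-subject factor can be fitted to the 36 MUD completers or to all 72. The aims point to the former, but the analysis section does not say so. The two choices estimate different quantities and have different power.

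Second, if the tests are made in MUD only, the data from 36 dosed and scanned controls enter no analysis described in the supplied text. Yet the chronic-use hypothesis is a statement about an interaction. A genotype effect that exists whether or not a person has MUD produces the same CV-over-WT difference within MUD. Of the data being collected, the control cells are what could show whether the genotype effect differs by diagnosis. A genotype-only model cannot confirm a pilot finding that was itself a group-by-genotype interaction.

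**Working it through.** **Inputs from the documents.** Four cells of 18, with 36 completers per diagnosis. The total reproduces: 4 × 18 = 2 × 36 = 72.

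**Assumed inputs.** The supplied text gives no significance level, target power, effect size or SD. Assumed here: two-sided 5%, a common SD of 1 for the subject-level measure, and genotype effects of 0.5, 0.8 and 1.0 SD.

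**Standard errors (in SD units).**
- Genotype pooled over diagnosis, 36 v 36: √(2/36) = 0.236, df 70.
- Genotype within MUD, 18 v 18: √(2/18) = 0.333, df 34.
- Diagnosis-by-genotype (difference of two differences): √(4/18) = 0.471, df 68.

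The last is 0.471/0.333 = 1.41 times the within-MUD standard error.

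**Case 1: the genotype effect exists only in MUD.** The pooled estimate averages the effect with zero, so 0.8 becomes 0.4. The noncentrality is 0.4/0.236 = 1.70 pooled and 0.8/0.333 = 2.40 within MUD. Power from the noncentral t distribution:

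| Effect in MUD (SD) | Pooled over 72 | Within MUD | Diagnosis-by-genotype |
|---|---|---|---|
| 0.5 | 18% | 31% | 18% |
| 0.8 | 39% | 65% | 39% |
| 1.0 | 55% | 83% | 55% |

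The pooled column assumes that MUD and controls have equal means. If diagnosis shifts the mean by D and is left out of the model, the residual SD is multiplied by √(1 + D²/4), which is 1.03, 1.12 or 1.25 for D = 0.5, 1 or 1.5. Pooled power is then lower still.

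**Case 2: the same genotype effect in both diagnoses (no interaction).** The within-MUD test is significant 31%, 65% or 83% of the time at 0.5, 0.8 or 1.0 SD, and the pooled test 55%, 92% or 99%. The diagnosis-by-genotype contrast is significant 5% of the time. These are ordinary power values at assumed effects, not rates of wrong conclusions. They show only that a CV-over-WT result does not discriminate between the two explanations.

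**Precision of the missing contrast.** 95% half-width at 18 per cell: 1.995 × 0.471 = 0.94 SD, against 2.032 × 0.333 = 0.68 SD within MUD. If the control SD is an assumed 0.7 or 0.5 of the MUD SD, the standard-error ratio √(1 + r²) is 1.22 or 1.12 and the half-width 0.81 or 0.75 MUD SD. If biorepository data raised every cell to an assumed 24 or 32 at equal variances, the half-width would be 0.81 or 0.70 SD.

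**The case against.** **Section 4.4 may give the controls a role.** This stands as a limit. A reader might infer that the controls have no role anywhere in the plan. The documents do not support that, because a cited section is missing; the statement holds for the supplied text only. If section 4.4 has a diagnosis term, it would have to be reconciled with the stated single between-subject variable.

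**A MUD-only test is coherent.** It is, and it is the natural reading of the aims. It would be wrong to say that the plan pools all 72. The point is that the analysis section does not settle the matter.

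**The interpretation is cautious.** A reader might infer that the plan treats CV over WT as proof of a chronic-use interaction. It claims only consistency, which is true of such a result. But the result is equally consistent with a genotype effect unrelated to MUD, and the plan does not mention that alternative.

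**The pilots make an equal effect in controls unlikely.** They lean that way. But PS2 rested on 24 controls, 9 of them CV, and 26 MUD participants in remission. The new study sets out to confirm and extend those findings.

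**The contrast would not prove the mechanism.** Correct. Diagnosis is not randomised, and the inclusion criteria require controls to have had at least one stimulant exposure. The contrast can show whether the genotype effect differs by diagnosis. It cannot by itself make chronic methamphetamine use the cause.

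**Conclusion.** The concern holds in limited form and should be fixed. In the supplied text the primary models carry genotype as the only between-subject variable, no hypothesis, model or contrast names the controls, and the analysis population is implied rather than stated. If a 0.8 SD effect exists only in MUD, pooling would cut power from about 65% to about 39%. If the tests stay within MUD, they are sound for a genotype difference in MUD, but the chronic-use reading is left without the contrast that both pilots tested.

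A reader should not conclude that the within-MUD tests of Hypotheses 1 to 3 are invalid; nothing here shows that. The standard-error ratio of 1.41 needs only equal cell sizes and variances. The power figures and half-widths also rest on the assumed level, effects, SD ratios and cell sizes. The size and diagnosis mix of the biorepository cohort are not given, so the analysed cells need not be 18.

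**What to change.** 1. State that the primary tests of Hypothesis 1 (genotype) and Hypotheses 2 and 3 (genotype by drug) are made within MUD. If one joint model is used instead, include diagnosis and its interactions, and let both the between-subject and the residual variance differ by diagnosis. Freeing the residual variance alone is not enough: each participant has a baseline scan at both Part 2 visits, so the genotype contrast also depends on between-subject variance.
2. Add the diagnosis-by-genotype contrast on baseline RSFC and craving as a stated secondary analysis using the controls. Report it with its 95% CI, and make the chronic-use reading in Interpretation of Results depend on it.
3. State that this contrast is imprecise, so non-significance is not evidence of no interaction. State also that it compares non-randomised groups whose controls have had stimulant exposure, so it cannot alone establish chronic use as the cause.
4. Say whether biorepository data enter these contrasts. If section 4.4 already has a diagnosis term, reconcile Specific Outcome Measures and Hypotheses with it.

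The cost is analysis wording: no new participants, visits or scans. Primary tests already intended as MUD-only do not change. A joint model spends a few more fixed-effect and variance parameters. The downside is a more cautious interpretation, resting on an openly imprecise estimate.
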